16.10. Study Exit

Study exit will typically occur either at the end of either Phase 1 (Eval #6), Phase 2 (Eval #11), or Phase 3 (Eval #16), based on the guidelines provided in Section 13. Study exit may occur earlier if the opioid reduction in a phase is not tolerable; if so, a final clinic visit will be scheduled to conduct the final assessments.

When the final follow-up visit is complete, the Investigator/coordinator will complete the study exit CRF. Adverse events unresolved at study exit will be followed by the Investigator until resolution occurs or at least 60 days after the subject's participation in the study is complete.

CONFIDENTIAL

All information contained in this document is confidential and is the sole property of Noctrix Health, Inc. Any reproduction in part or whole without the written permission of Noctrix Health, Inc. is prohibited.

 NOCTRIX HEALTH	Clinical Trial Investigational Plan, Protocol CT-03 (Opioid Reduction Study)	Document #: CT-2 (Previously CT-03) Rev: 4.0 (Superseded Rev C) CC#: 720 (Previously DCO #138) Effective: 09/24/2021
---	---	---

Both IRLS and CGI-I will be administered at study exit.

16.11. Extension Phase

Subjects who tolerate Phases 1 and 2 without a clinically significant increase in RLS symptoms and are at a non-zero dose of opioids will have the option to complete an extension phase consisting of an additional reduction in opioid dose.

16.12. Subject Discontinuation

A subject may be removed from the study prior to completion for any of the following reasons:

- Voluntary withdrawal of consent
- Adverse event preventing further study participation
- Investigator believes risk of further subject participation outweighs benefit
- Persistent non-compliance or lost to follow-up
- Pregnancy
- Subject no longer meets inclusion criteria
- Reduced opioid dosage is not tolerable, as evaluated by the subject or the investigator
- Subject fails to comply with reduced opioid dosage
- Subject changes dosage of non-opioid medications known to interfere with sleep or RLS symptoms, including sleep medications, antidepressants, sedative antihistamines.

The Investigator or research staff will complete a study exit form in the CRF for any subject who prematurely discontinues from the study. If discontinuation was the result of an AE, the AE will also be recorded in the CRF.

Upon discontinuation, subjects will receive partial compensation commensurate with their completed Phases.

16.13. Study Termination

The Sponsor may terminate the study as a whole or at individual study sites under the following circumstances:

- Suspicion of risk to subjects, including occurrence of high rate of known AEs or unexpectedly high rate of unexpected AEs

CONFIDENTIAL

All information contained in this document is confidential and is the sole property of Noctrix Health, Inc.
Any reproduction in part or whole without the written permission of Noctrix Health, Inc. is prohibited.

 NOCTRIX HEALTH	Clinical Trial Investigational Plan, Protocol CT-03 (Opioid Reduction Study)	Document #: CT-2 (Previously CT-03) Rev: 4.0 (Superseded Rev C) CC#: 720 (Previously DCO #138) Effective: 09/24/2021
---	---	---

- Poor site compliance with the study protocol
- Inadequate site enrollment
- Obtaining new scientific knowledge that shows that the study is no longer valid or necessary
- Persistent non-compliance with IRB or regulatory requirements
- Persistent failure to comply with obligations arising from the clinical trial agreement
- Other business reasons (e.g., insolvencies or business entity liquidation)

The sponsor will document reasons for study suspension and notify relevant site Investigators and governing IRBs. If suspension occurred because of a safety issue, all Investigators will be notified. When terminating the study, the sponsor and Investigator will assure that adequate consideration is given to the protection of the subjects' interests.

17. Study Endpoints

17.1. Efficacy

In the absence of an adjunctive treatment, a reduction in opioid dose will cause an increase in RLS symptoms. The efficacy of NPNS will be assessed by its capacity to prevent this increase in RLS symptoms. Subjects who discontinue due to nonspecific opioid withdrawal symptoms will not be included in the efficacy analysis but will be considered in the safety analysis. Efficacy endpoints will be calculated during the Assessment period except in cases of dropout during the run-in period(s); Section 13.2 describes how efficacy endpoints will be calculated in cases of dropout during the run-in period(s).

17.1.1. Efficacy Endpoints

Endpoint 1 (Primary Endpoint): Percentage of subjects without a clinically significant increase in RLS symptoms (i.e. CGI-I score of 5 or less relative to baseline) during the first Phase involving an opioid dose reduction of $\geq 20\%$ relative to baseline.

Endpoint 2: Percentage of subjects without a clinically significant increase in RLS symptoms (i.e. CGI-I score of 5 or less relative to baseline) during the first Phase involving an opioid dose reduction of $\geq 1/3$ relative to baseline.

Endpoint 3: IRLS during the first Phase with an opioid dose reduction of $\geq 20\%$ relative to baseline.

Endpoint 4: IRLS during the first Phase with an opioid dose reduction of $\geq 1/3$ relative to baseline.

CONFIDENTIAL

 NOCTRIX HEALTH	Clinical Trial Investigational Plan, Protocol CT-03 (Opioid Reduction Study)	Document #: CT-2 (Previously CT-03) Rev: 4.0 (Superseded Rev C) CC#: 720 (Previously DCO #138) Effective: 09/24/2021
---	---	---

Endpoint 5: Maximal percentage reduction in opioid dose relative to baseline associated with a CGI-I score of 5 or less, averaged across subjects.

Of the 5 efficacy endpoints, only Endpoint 5 considers data during the Extension phase.

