Study Design	
The flowchart details the study design:
 
Opioid-treated RLS patients undergo Consent, screening, and NPNS training.They enter Phase 1, >=20% opioid dose reduction, which includes a NPNS 1-2 wk Run-in period and a NPNS 1-wk Assessment period. A CGI-I rating is taken during the assessment period. If CGI-I > 5, the patient is Not tolerated and the study ends. If CGI-I of 5 or less, they proceed to Phase 2, >=33% opioid dose reduction relative to baseline.Phase 2 follows the same structure: NPNS 1-2 wk Run-in period and NPNS 1-wk Assessment period. If CGI-I > 5, the patient is Not tolerated and the study ends. If CGI-I of 5 or less, they enter the Optional Extension Phase.The Optional Extension Phase involves NPNS 1-2 wk Run-in period and NPNS 1-wk Assessment period. If CGI-I > 5, the patient is Not tolerated and the study ends. 
An iterative opioid dose reduction is performed in conjunction with open-label NPNS administration. For each of the two step-downs in opioid dose (Phase 1 and Phase 2), a 1-2-wk run-in period is followed by a 1-wk assessment period. The run-in period is to ensure that any opioid withdrawal symptoms unrelated to RLS have resolved and to confirm the appropriate instructions for NPNS usage (e.g. timing and intensity). Study participation is terminated at the first phase that leads to a clinically significant

CONFIDENTIAL

 NOCTRIX HEALTH	Clinical Trial Investigational Plan, Protocol CT-03 (Opioid Reduction Study)	Document #: CT-2 (Previously CT-03) Rev: 4.0 (Superseded Rev C) CC#: 720 (Previously DCO #138) Effective: 09/24/2021
---	---	---

	
increase in RLS severity or is otherwise not tolerated. Participants who tolerate both phases may have the option of an extension phase involving a third reduction in opioid dose.

Study Population	
Adults with moderate-to-severe primary Restless Legs Syndrome (RLS) who are taking a stable dose of prescription opioids to treat RLS.

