13.1 Accounting for between-subjects variation in starting opioid dose

The study has been designed to account for between-subjects variation in the starting dose and quantal dose of opioid medication, while also allowing calculation of standardized efficacy endpoints. The opioid dose reduction process is complicated by that fact that there are quantal doses of opioid medication. For example, for methadone, which is commonly prescribed for RLS, the minimum pill size is 5mg and the quantal size is 2.5mg because pills can be broken in half.

All subjects initially participate in Phase 1, which involves the smallest reduction in opioid dose of greater than or equal to 20% of the starting dose. Subjects who tolerate Phase 1 without a clinically significant increase in RLS symptoms will advance to Phase 2, which involves the smallest additional reduction in opioid dose that also represents a total reduction of greater than or equal to 1/3 of the starting dose. Subjects who tolerate Phase 2 without a clinically significant increase in RLS symptoms will have the option to complete Phase 3, which involves an additional reduction in opioid dose. Once the subject completes a Phase where no further reduction is possible (e.g. a subject reaches 0mg in Phase 1 or 2), they will complete the study at the end of that Phase.

For example, in the case of methadone, the minimal quantal dose reduction is 2.5mg. Therefore, for methadone (**Table 4**):

- a subject on a 10mg starting dose would reduce to 7.5mg (25% reduction) in Phase 1 and 5.0mg (50% total reduction) in Phase 2. The endpoints related to $\geq 20\%$ reduction would be evaluated in Phase 1 and the endpoints related to $\geq 1/3$ reduction would be evaluated in Phase 2.
- a subject on a 7.5mg starting dose would reduce to 5.0mg (1/3 reduction) in Phase 1 and 2.5mg (2/3 total reduction) in Phase 2. The endpoints related to both $\geq 20\%$ reduction and $\geq 1/3$ reduction would be evaluated in Phase 1.
- a subject on a 5.0mg starting dose would reduce to 2.5mg (50% reduction) in Phase 1 and 0mg (100% total reduction) in Phase 2. The endpoints related to both $\geq 20\%$ reduction and $\geq 1/3$ reduction would be evaluated in Phase 1.
- a subject on a 2.5mg starting dose would reduce to 0mg (100% reduction) in Phase 1 and complete the study at the end of Phase 1. The endpoints related to both $\geq 20\%$ reduction and $\geq 1/3$ reduction would be evaluated in Phase 1.

CONFIDENTIAL

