16.5. Baseline Assessments

The participant completes an IRLS questionnaire describing their symptoms and experiences over the past week and a demographic/characterization assessment including questions about their history of RLS symptoms and medication(s).

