17.1.3. Efficacy Analysis

Endpoints 1 and 2 are calculated with the following formula, respectively for Phases 1 and 2:

$100\% * ((X - Y) / (N - M))$, where

- N = Number of subjects who entered the Run-in period for the Phase.
- M = Number of subjects excluded during Run-in period due to non-RLS opioid withdrawal symptoms.
- Y = Number of subjects excluded during Run-in period primarily due to intolerable RLS symptoms.
- X = Number of subjects who complete Assessment period with no clinically significant worsening in Clinical Global Impression-Improvement scale (CGI-I) relative to Baseline, where a clinically significant worsening is defined by a score of 6 (Much worse) or 7 (Very much worse).

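### Efficacy Endpoints 3 and 4 are raw IRLS scores, so they do not measure the increase in RLS symptoms that section 17.1 sets out to prevent; Endpoint 4 is also partly restricted to subjects who tolerated Phase 1

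*Combined protocol and SAP*

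**What the plan says.** Section 17.1 starts from the premise that "In the absence of an adjunctive treatment, a reduction in opioid dose will cause an increase in RLS symptoms", and then states that "The efficacy of NPNS will be assessed by its capacity to prevent this increase in RLS symptoms". The target is therefore a change in symptoms from the pre-reduction state.

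The two IRLS endpoints in section 17.1.1, repeated in the synopsis, are "Endpoint 3: IRLS during the first Phase with an opioid dose reduction of" at least 20%, and "Endpoint 4: IRLS during the first Phase with an opioid dose reduction of" at least one third, each relative to baseline. Endpoints 1 and 2 refer to baseline twice, once for the CGI-I and once for the dose. Endpoints 3 and 4 refer to it once, for the dose.

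Section 17.1.3 supplies a calculation for the first two endpoints only: "Endpoints 1 and 2 are calculated with the following formula, respectively for Phases 1 and 2". No section gives a change score, pairing, summary statistic or threshold for IRLS. Section 17.5 only permits unspecified exploratory analysis.

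A baseline IRLS exists. Section 16.5 says "The participant completes an IRLS questionnaire describing their symptoms and experiences over the past week", and Table 5A marks IRLS at Eval 1.

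On who reaches Phase 2, section 13.1 says "Subjects who tolerate Phase 1 without a clinically significant increase in RLS symptoms will advance to Phase 2". The synopsis says "Study participation is terminated at the first phase that leads to a clinically significant" worsening of RLS.

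**The concern.** Every subject knowingly receives active stimulation (section 14) and there is no comparator, so a symptom score can be judged only against the subject's own starting point. The inclusion criteria in section 4.1 set no IRLS range, so a Phase mean has no implied anchor either. According to section 16.9 the CGI-I is completed by the investigator or designee and the IRLS by the subject. IRLS is thus the only subject-completed symptom score among the efficacy endpoints, and it is the one not expressed as a change.

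Endpoint 4 has a second difficulty. A subject who needs Phase 2 to reach one third contributes only after tolerating Phase 1. If the raw mean is read against the baseline mean of everyone enrolled, the two means describe different subjects. What is at stake is the reading of two secondary results, not whether the study passes.

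**Working it through.** The plan states no figure for Endpoints 3 or 4, and no IRLS standard deviation, correlation or Phase 1 failure rate, so there is nothing to reproduce. Three checks follow. Only the second uses figures from the documents; the IRLS values in the others are assumed.

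**1. Does a raw Phase mean identify the increase?** Increase = Phase mean − baseline mean of the same subjects. For an assumed Phase mean of 20:

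- baseline 14: 20 − 14 = +6
- baseline 17: 20 − 17 = +3
- baseline 20: 20 − 20 = 0
- baseline 23: 20 − 23 = −3

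The same endpoint value fits worsening, no change and improvement.

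**2. In which Phase does Endpoint 4 fall?** Inputs are the 2.5 mg methadone step and the rules in section 13.1 and Table 3. Phase 1 is the smallest reduction of at least 20%. Phase 2 is the smallest further reduction totalling at least one third. Reduction after k steps = 2.5k / starting dose.

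| Start (mg) | Phase 1 | Phase 2 | Endpoint 4 falls in |
|---|---|---|---|
| 20 | 5/20 = 25.0% | 7.5/20 = 37.5% | Phase 2 |
| 17.5 | 5/17.5 = 28.6% | 7.5/17.5 = 42.9% | Phase 2 |
| 15 | 5/15 = 33.3% | 7.5/15 = 50.0% | Phase 1 |
| 12.5 | 2.5/12.5 = 20.0% | 5/12.5 = 40.0% | Phase 2 |
| 10 | 2.5/10 = 25.0% | 5/10 = 50.0% | Phase 2 |
| 7.5 | 2.5/7.5 = 33.3% | 5/7.5 = 66.7% | Phase 1 |
| 5 | 2.5/5 = 50.0% | 5/5 = 100% | Phase 1 |
| 2.5 | 2.5/2.5 = 100% | none | Phase 1 |

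The percentages agree with Table 4. Four of the eight starting doses reach one third only after the Phase 1 tolerance requirement. For the other four, Endpoint 4 is the same Phase 1 score as Endpoint 3. Endpoint 4 therefore pools selected and unselected subjects. The share of subjects in each group is not given.

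**3. What does the selection do?** Assume 20 subjects with baseline mean 16, all needing Phase 2, of whom 8 leave in Phase 1 and 12 continue and each rise by 2. Continuers' baseline = (20 × 16 − 8 × leavers' baseline) / 12.

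- Leavers 20: continuers (320 − 160)/12 = 13.3; raw Endpoint 4 = 15.3; minus 16 = −0.7
- Leavers 16: continuers 16; raw 18.0; minus 16 = +2.0
- Leavers 12: continuers (320 − 96)/12 = 18.7; raw 20.7; minus 16 = +4.7

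The paired change is +2.0 in all three. The raw comparison can understate, match or overstate it, and nothing in the documents says which applies.

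Pairing does not undo the selection. A simulation of 400,000 subjects assumed baseline mean 20, between-subject SD 6, SD of individual change 4, error SD 3, and true mean rises of 3 (Phase 1) and 5 (Phase 2). A Phase 1 failure was an observed IRLS rise above a cut-off, standing in for a CGI-I above 5.

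| Failure cut-off | Enter Phase 2 | Raw mean, entrants vs all continuing | Change, entrants vs all continuing |
|---|---|---|---|
| rise > 6 | 70% | 23.6 vs 25.0 | +2.9 vs +5.0 |
| rise > 8 | 80% | 24.1 vs 25.0 | +3.5 vs +5.0 |

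Change from baseline makes the endpoint measure the increase among those observed. It remains too favourable as an estimate for everyone who started.

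**The case against.** The case for leaving the plan alone has real content. These are non-primary endpoints of a study titled exploratory, without a test or threshold. The only efficacy success criterion is Endpoint 1 above 50% (section 17.1.5). Endpoints 1 and 2 already capture worsening relative to baseline through the CGI-I. For Endpoint 3 everyone enters Phase 1, so there is no selection on CGI-I. When the same subjects contribute at both times, mean IRLS minus their mean baseline equals the mean paired change, and the data to compute it will exist. All of that stands, and it limits the consequence. It does not supply the missing definition: the plan never says that the comparison will be made, in which subjects, or with what interval.

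Three stronger readings are tempting, and the documents do not support them.

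- A reader might infer that raw Endpoint 4 will show false improvement. That requires leavers to have had higher baselines. Advancement depends on CGI-I relative to baseline, and nothing links that to baseline severity. The sign can reverse, as shown above.
- A reader might infer a definite loss of precision. With n = 20, assumed SD 6–8 and within-subject correlation 0.5–0.7, a paired interval is 27–43% narrower than one treating the two means as independent. No section plans that unpaired comparison, so this is not a cost of the plan.
- A reader might infer that change from baseline cures the selection. It does not. In the simulation the change among entrants falls 2.1 points short (5.0 − 2.9), against 1.4 for the raw mean (25.0 − 23.6).

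One caution affects the remedy. Sections 13.2 and 17.1 let the exit IRLS of RLS-related run-in dropouts count. A change score limited to Assessment-period values would drop them, and they are likely to be among the worst RLS outcomes.

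**Conclusion.** The point holds on the text. Followed as written, Endpoints 3 and 4 report a symptom level, while section 17.1 asks about an increase, and the only available reference is collected but enters neither definition. For 4 of the 8 tabulated methadone starting doses, Endpoint 4 also describes only subjects who tolerated Phase 1, so its raw mean should not be set beside the full-sample baseline mean.

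The count of four rests on instructed doses under Table 4. Other opioids may split differently, and section 17.1.2 uses the dose actually taken. The size and direction of the mismatch cannot be derived from the documents; every IRLS value above is assumed and shows mechanism only. No pass/fail result changes. The amendment is worth making because it aligns two endpoints with the stated objective at almost no cost.

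**What to change.** In section 17.1.1 and the synopsis, define Endpoints 3 and 4 as the within-subject change in IRLS from Eval 1 to the qualifying Phase. Use the Assessment-period value or, for subjects who leave during run-in because of RLS symptoms, the exit IRLS, as sections 13.2 and 17.1 already provide.

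In section 17.1.3, add that the mean change will be reported with a paired 95% CI, the number contributing and those subjects' own baseline mean. Keep raw scores as descriptive output.

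For Endpoint 4, state that the result is conditional on entering Phase 2 for subjects who first reach one third there, and show them separately from subjects assessed in Phase 1. Add a sensitivity analysis that brings in the exit IRLS of Phase 1 failures, which section 16.10 already collects. Note that those values were recorded at a smaller reduction than one third, so they stand in for an unobserved outcome.

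The cost is a few sentences and one extra table. No visit, questionnaire or subject is added. The one thing to guard against is wording that confines the change score to Assessment-period values and so loses the RLS-related run-in dropouts.

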11.2. Sponsor Responsibilities

Listed below are the Sponsor's responsibilities for this study.

- a) Assure IRB approval of protocol and informed consent is obtained.
- b) Select and train monitors.
- c) Select investigators.

CONFIDENTIAL

All information contained in this document is confidential and is the sole property of Noctrix Health, Inc.

Any reproduction in part or whole without the written permission of Noctrix Health, Inc. is prohibited.

 NOCTRIX HEALTH	Clinical Trial	Document #: CT-2 (Previously CT-03) Rev: 4.0 (Superseded Rev C) CC#: 720 (Previously DCO #138) Effective: 09/24/2021
	Investigational Plan, Protocol CT-03 (Opioid Reduction Study)	

- d) Train investigators in device use.
- e) Obtain Agreement Letter and curriculum vitae and proof of appropriate licensure of investigator and other study staff.
- f) Control shipment of investigational devices.
- g) Conduct day-to-day administration of study.
- h) Investigate unanticipated, device related adverse effects.
- i) Document protocol deviations and violations.
- j) Obtain statement of financial disclosure.
- k) Administer, assist, and/or oversee calibration for each subject.

12. Duration

The study will be completed a maximum of 18 months after the study opens to enrollment.

13. Study design

The study design consists of iterative opioid dose reduction relative to baseline opioid dose (the week prior to study entry). Each Phase of the study includes NPNS usage and an opioid dosage reduction as shown in Table 3 below. As discussed in Section 13.1, the baseline opioid dose will partly determine whether a subject is eligible to continue to Phases 2 and 3.

- Phase 1 involves a total reduction in opioid dose of $\geq 20\%$ relative to the starting dose.
- Phase 2 involves a total reduction in opioid dose of $\geq 1/3$ relative to the starting dose.
- Optional phase 3 involves a further reduction in opioid dose.

Table 3. Study design phases

Phase	Duration	Description	Opioid dosage Reduction relative to baseline	NPNS usage	Efficacy endpoint evaluation
1	1-2 wks	Run-in	Smallest reduction of $\geq 20\%$ relative to baseline	Yes	No
	1-wk	Assessment		Yes	Yes
2	1-2 wks	Run-in	Smallest total reduction of $\geq 1/3$ relative to baseline that is also a reduction relative to Phase 1	Yes	No
	1-wk	Assessment		Yes	Yes
3 (optional)	1-2 wks	Run-in	Additional reduction relative to Phase 2	Yes	No
	1-wk	Assessment			

CONFIDENTIAL

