13.2 Run-in and Assessment periods

[figure not shown]
Each Phase involves a 1-2 week run-in period followed by a 1-week assessment period. Assessment periods are primarily designed for endpoint evaluation. Run-in periods are designed for two reasons: (i) to provide a run-in phase to optimize instructions for NPNS device self-administration (e.g. timing and intensity) and (ii) so that any opioid withdrawal symptoms unrelated to the RLS condition resolve prior to the assessment period. Each run-in period will last a minimum of 1-week and a maximum of 2-weeks.

The investigator is permitted to adjust the instructed schedule of opioid medication and/or NPNS usage during a Step-Down based on clinical evaluation of response to opioid treatment and NPNS.

CONFIDENTIAL

All information contained in this document is confidential and is the sole property of Noctrix Health, Inc.
Any reproduction in part or whole without the written permission of Noctrix Health, Inc. is prohibited.

Figure 1. Flowchart of Run-in and Assessment periods for Phases 1 & 2

Additionally:

[figure not shown]
- If clinically significant opioid withdrawal symptoms unrelated to RLS become intolerable during the run-in period for a given Phase, participation will be discontinued and data from the subject will not count towards the efficacy endpoints for that Phase.
- If opioid withdrawal symptoms related to RLS become intolerable at any point during a run-in period, participation will be discontinued and the subject will count towards the efficacy endpoints for that Phase.
- The investigator may decide that participation should be discontinued at any time if there are excessive opioid withdrawal symptoms, even if those symptoms are tolerable.
- If opioid withdrawal symptoms become intolerable mid-week during a run-in period, participation will be discontinued.
- In all cases, efficacy outcome measures CGI-I and IRLS will be assessed at study exit but will not be included in analysis of the efficacy endpoints unless opioid withdrawal symptoms related to RLS was the primary reason for discontinuation.
- The Extension Phase is optional and requires approval by both the investigator and the participant. The structure of this phase is similar phases 1 and 2.

CONFIDENTIAL

All information contained in this document is confidential and is the sole property of Noctrix Health, Inc.
 Any reproduction in part or whole without the written permission of Noctrix Health, Inc. is prohibited.

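### Endpoint 5 is a single mean that mixes tolerance of opioid reduction with starting-dose mix and uptake of the optional Extension

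*Combined protocol and SAP*

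**What the plan says.** Section 17.1.1 defines "Endpoint 5: Maximal percentage reduction in opioid dose relative to baseline associated with a CGI-I score of 5 or less, averaged across subjects". It adds: "Of the 5 efficacy endpoints, only Endpoint 5 considers data during the Extension phase".

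The doses come from Section 13. Every subject starts in Phase 1, "which involves the smallest reduction in opioid dose of greater than or equal to 20% of the starting dose". Table 3 sets Phase 2 as the smallest total reduction of at least one third "that is also a reduction relative to Phase 1". For Phase 3, Table 3 says only "Additional reduction relative to Phase 2", with no size. Section 13.2 states: "The Extension Phase is optional and requires approval by both the investigator and the participant". Sections 13.1 and 16.11 open the Extension only to subjects who tolerated Phases 1 and 2 and are still on a non-zero dose.

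Section 13.1 recognises that tablets come in fixed steps, 2.5 mg for methadone, and works through examples. One is that "a subject on a 5.0mg starting dose would reduce to 2.5mg (50% reduction) in Phase 1 and 0mg (100% total reduction) in Phase 2". Its examples assign the 20% and one-third endpoints to Phases. Neither 13.1 nor 17.1 has a rule that separates starting dose or Extension uptake from tolerance in Endpoint 5.

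**The concern.** Section 3 asks whether the response to NPNS is large enough to allow a clinically significant reduction in opioid dose. Endpoint 5 is the only efficacy endpoint that measures the size of the reduction, so readers will turn to it for that answer.

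Two things other than tolerance move it. Fixed tablet steps and two main Phases give each starting dose its own maximum percentage through Phase 2. The Extension then allows a higher score, but only for those who are eligible, willing and approved. With 20 to 40 subjects and one overall mean, a reader cannot tell whether a high or low figure reflects tolerance, the starting doses enrolled, or Extension uptake.

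**Working it through.** **Inputs.** The step is 2.5 mg (Section 13.1, methadone example). Starting doses are the eight rows of Table 4. The Phase 1 and Phase 2 rules are those of Section 13.1 and Table 3. A Phase counts as tolerated at CGI-I of 5 or less (Section 17.1.1).

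**Formula.** Percentage reduction after k steps = 100 × k × 2.5 / starting dose. Phase 1 uses the smallest k giving at least 20%. Phase 2 uses the smallest larger k giving at least 33.3%.

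**Reproducing the plan.** This formula returns every cell of Table 4 to rounding, and the Phase rules return all four worked examples in Section 13.1 (10, 7.5, 5 and 2.5 mg).

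**Maximum score in Phases 1 and 2, everything tolerated.**

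| Start (mg) | Phase 1: mg removed (%) | Phase 2: mg removed (%) | Maximum through Phase 2 |
|---|---|---|---|
| 20 | 5.0 (25.0) | 7.5 (37.5) | 37.5% |
| 17.5 | 5.0 (28.6) | 7.5 (42.9) | 42.9% |
| 15 | 5.0 (33.3) | 7.5 (50.0) | 50.0% |
| 12.5 | 2.5 (20.0) | 5.0 (40.0) | 40.0% |
| 10 | 2.5 (25.0) | 5.0 (50.0) | 50.0% |
| 7.5 | 2.5 (33.3) | 5.0 (66.7) | 66.7% |
| 5 | 2.5 (50.0) | 5.0 (100) | 100% |
| 2.5 | 2.5 (100) | none: dose is 0 mg | 100% |

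The range is 100 / 37.5 = 2.67-fold at identical, complete tolerance. It is not monotone: 12.5 mg gives 40% and 15 mg gives 50%.

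**Effect of starting-dose mix.** Take 20 subjects, all tolerating every main Phase, with no Extension. Only starting doses worked out in Section 13.1 are used.
- Twenty at 10 mg: 20 × 50 / 20 = 50%.
- Ten at 2.5 mg and ten at 10 mg: (10 × 100 + 10 × 50) / 20 = 75%.

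Mean dose removed is 5.0 mg/day in the first cohort and (10 × 2.5 + 10 × 5.0) / 20 = 3.75 mg/day in the second.

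**Effect of Extension uptake.** Endpoint 5 takes each subject's largest tolerated percentage. A failed Extension leaves the Phase 2 score in place and a tolerated one raises it, so uptake cannot lower the mean. Because the step is not stated, the effect is a range. For a cohort all starting at 10 mg, with uptake u and every step tolerated:
- Step of 2.5 mg (assumed): mean = 50 + 25u, from 50% at u = 0 to 75% at u = 1.
- Reduction to 0 mg (assumed): mean = 50 + 50u, from 50% to 100%.

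**Removing the Extension is not enough.** The table already excludes it, and the dependence on starting dose remains.

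**The case against.** The strongest case against is about consequence. The study is labelled exploratory, efficacy success rests on Endpoint 1 alone (Section 17.1.5), and Endpoint 5 has no success criterion. Percentage reduction from baseline is a legitimate measure, and Section 17.1.1 does not claim that the score is the most a subject could have tolerated. All of this stands. It also stands that Table 4 is an example for one drug, that other opioids are eligible, and that Section 17.1.2 uses the dose actually reported, so real scores need not fall on this grid.

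Four stronger readings are tempting, and the documents do not support them.

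- A reader might infer that a smaller, worse-tolerated reduction can score twice as high. Take one cohort at 20 mg tolerating both Phases (37.5%, 7.5 mg/day removed) and one at 5 mg with half failing Phase 2: (50 + 100) / 2 = 75%, with (2.5 + 5.0) / 2 = 3.75 mg/day removed. The ratio of 2.0 assumes that nobody in the first cohort enters the Extension, although all are eligible. One 2.5 mg step gives 50% and a ratio of 1.5; going to 0 mg gives 100% and reverses the order. The reduction is smaller only in milligrams. The 20 mg start also assumes eligibility under the 60 MME limit, and the documents give no conversion factor.
- A reader might infer that the mean reports mainly dose mix and uptake. Nothing shows this: the documents give neither a starting-dose distribution nor an expected uptake, and tolerance does move the score.
- A reader might infer a contradiction with Section 13.1's phrase "while also allowing calculation of standardized efficacy endpoints". That phrase is general, the section's examples concern the threshold endpoints, and it never names Endpoint 5.
- A reader might infer that pooled MME removed over pooled baseline MME would be a better headline. In the two cohorts above that ratio is still 37.5% against 75%. Absolute milligrams are also capped by starting dose: a 2.5 mg subject cannot remove more than 2.5 mg.

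**Conclusion.** The point holds as a limit on interpretation. Through Phases 1 and 2, complete tolerance scores between 37.5% and 100% across the Table 4 starting doses. At full tolerance with no Extension, the starting-dose mix alone can move the mean from 50% to 75%. For a 10 mg cohort tolerating every step, full Extension uptake adds 25 percentage points if the step is 2.5 mg and 50 if it goes to 0 mg.

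These figures rest on the methadone example, on its 2.5 mg step, and on subjects taking the instructed doses. The 50% against 75% comparison uses only starting doses worked through in Section 13.1. The maximum is fixed by starting dose only through Phase 2; beyond that it is undefined because the Phase 3 step is not quantified. No decision rule changes, and how far the effect reaches in practice depends on the doses enrolled and the uptake seen.

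**What to change.** Keep the percentage and amend Sections 17.1.1 and 17.1.3 to report Endpoint 5 as follows.

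1. Give it for Phases 1 and 2 only and, separately, including the Extension. Beside the second figure, state how many subjects were eligible for the Extension, entered it and tolerated it.
2. Show it in a few broad starting-dose groups, each beside the maximum percentage attainable in Phases 1 and 2 for the subjects in it, worked out from their own opioid and tablet step under Section 13.1. Eight separate doses would leave on average 2.5 to 5 subjects each (20/8 to 40/8), so the groups must be broad and fixed in advance.
3. Add mean absolute reduction in MME per day as a supplementary descriptive figure, not as a replacement for the percentage.

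The data are already collected, and MME is already needed for the eligibility limit in Section 4.1. No visit, procedure or dose changes. The cost is one extra descriptive table with small groups, and a Phases 1 and 2 figure that will be no higher than the current one and may be lower.
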